^d The Day 1 Visit should be on the same day as the last scheduled visit of the parent study (Section 9.1.1). Subjects whose Day 1 Visit is NOT within 1 day of the last scheduled visit of the parent study will repeat all Day 1 assessments. Subjects whose Day 1 Visit is within 1 day of the last scheduled visit of the parent study will NOT have to repeat any Day 1 assessments that were specified to be performed at the last scheduled visit in the parent study.

Table 3-1 Study VX20-445-119: Treatment Period and Safety Follow-up Visit									
Event/ Assessment ^a	Treatment Period					ETT Visit ^b	Safety Follow-up Visit (28 ± 7 Days After Last Dose of Study Drug ^c)	Comments	
	Day 1 ^d	Weeks 4, 8, 16, 24 (± 5 Days)	Weeks 12, 20, 28, 32, 40, 44, 52, 56, 64, 68, 76, 80, 88, 92 (± 5 Days)	Weeks 36, 48, 60, 72, 84 (± 5 Days)	Week 96 (± 10 Days)				
Standard 12-lead ECG	X	Weeks 8, 16, 24		Weeks 48, 72	X	X	X	Performed prior to any procedure that may affect heart rate (e.g., blood draws) and after subject has been at rest for at least 5 minutes (Section 11.4.5).	
Sweat chloride	X	X		Weeks 48, 72	X	X		Section 11.2.1	
Multiple-breath washout	X	X		Weeks 48, 72	X	X		Performed in multiple replicates, pre-bronchodilator, before the AM dose, and before spirometry assessment (Section 11.2.1).	
Spirometry	X	X		X	X	X	X	Performed pre-bronchodilator, before the AM dose, and at approximately the same time at each visit (Section 11.2.3).	
Pregnancy test	Urine	Serum	Urine	Serum	Serum	Serum	Serum	For all female subjects at telephone contacts, a urine pregnancy test will be performed with a home kit provided by the study site. Results of the home pregnancy test will be reported to the site by telephone (Section 11.4.2).	
Serum chemistry	X	X		X	X	X	X	Section 11.4.2	
Hematology	X	X		X	X	X	X		
Coagulation	X	Week 24		Weeks 48, 72	X	X			
Urinalysis	X			Week 48	X	X			
AEs and SAEs	Continuous from signing of the ICF through completion of study participation								Section 13.1; Completion of study participation is defined in Section 9.1.5.

Table 3-1 Study VX20-445-119: Treatment Period and Safety Follow-up Visit								
Event/ Assessment ^a	Treatment Period					ETT Visit ^b	Safety Follow-up Visit (28 ± 7 Days After Last Dose of Study Drug ^c)	Comments
	Day 1 ^d	Weeks 4, 8, 16, 24 (± 5 Days)	Weeks 12, 20, 28, 32, 40, 44, 52, 56, 64, 68, 76, 80, 88, 92 (± 5 Days)	Weeks 36, 48, 60, 72, 84 (± 5 Days)	Week 96 (± 10 Days)			

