12.3.3.2 Analysis of Secondary Efficacy and Pharmacodynamic Endpoints

The Secondary Endpoints include:

- **Absolute change from baseline in SwCl**

The analysis of this endpoint will be performed using a mixed-effects model for repeated measures (MMRM) with absolute change from baseline in SwCl at each post-baseline visit in this current open-label study as the dependent variable. The model will include the parent study treatment group, visit, and parent study treatment-by-visit interaction as fixed effects, and will be adjusted for main covariates as appropriate. The least squares (LS) mean estimate with a 2-sided 95% CI at each visit will be provided.

- **Absolute change from baseline in LCI_{2.5}**

Analysis of this efficacy endpoint will be based on a MMRM model similar to the analysis of the absolute change from baseline in SwCl.

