8.3.2.2 Analysis Method

Absolute change in SwCl from baseline:

The mixed-effects model for repeated measures (MMRM) for the parent study 116-FAS will be same as that described in the SAP for Study 116. In the MMRM for the OL-FAS, the absolute change from baseline in SwCl will be the dependent variable. The model will include treatment group (as randomized in the parent study), visit, and treatment-by-visit interaction as fixed effects, with continuous baseline LCI_{2.5} from the parent study and weight at Screening (<30 versus ≥30 kg) of the parent study as covariates.

The repeated-measures analysis will be based on the restricted maximum likelihood method assuming an unstructured covariance structure to model the within-subject errors. The denominator degrees of freedom will be based on the method proposed by Kenward-Roger⁶. If the model fails to converge due to the unstructured covariance assumption, a compound symmetry covariance structure will be used to model the within-subject errors. In the MMRM approach, assuming that the data are missing at random, no imputation of missing data will be performed.

Results from the 2 MMRMs (for the parent study and for the OE) will be presented in a single summary table. The number of subjects, least-squares means (LS means) for absolute change from baseline at scheduled visits within each treatment group (as randomized in the parent study) along with the corresponding standard error (SE), and 95% confidence interval (CI) will be presented. The LS means (±SE) for absolute change from baseline at each visit will also be plotted by treatment group (as randomized in the parent study).

In addition, the descriptive statistics for raw values and absolute changes from baseline by treatment group (as randomized in the parent study) and OL visit will be presented for the OL-FAS.

Absolute change in LCI_{2.5} from baseline:

Analysis of this endpoint will be based on an MMRM similar to the analysis of the absolute change from baseline in SwCl. A descriptive summary of raw values and absolute changes from baseline will also be presented.

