8.3.3.2 Analysis Method

Absolute change in ppFEV₁ from baseline:

Analysis of this endpoint will be based on an MMRM similar to the analysis of the absolute change in SwCl. A descriptive summary of raw values and absolute changes from parent study baseline will also be presented.

The primary analysis will use the spirometry data obtained at clinic only. An additional analysis may be performed to include all available spirometry data obtained at clinic and obtained at home, if the spirometry data obtained at home are assessed to be reasonably consistent with the spirometry data obtained at clinic.

Absolute change in CFQ-R respiratory domain (RD) score from baseline:

Analysis of this endpoint will be based on an MMRM similar to the analysis of the absolute change in SwCl. A descriptive summary of raw values and absolute changes from parent study baseline will also be presented. In addition, the descriptive summary for raw values and the absolute change from parent study baseline of the parent version's CFQ-R RD score will be presented.

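### If the unstructured MMRM does not converge, the SAP drops straight to compound symmetry, so visit-specific standard errors and 95% CIs can be wrong in either direction.

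*SAP*

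**What the plan says.** SAP 8.3.2.2 (sweat chloride, SwCl) uses the "restricted maximum likelihood method assuming an unstructured covariance structure to model the within-subject errors". The fallback is a single step: if that structure prevents convergence, "a compound symmetry covariance structure will be used to model the within-subject errors". On inference, "The denominator degrees of freedom will be based on the method proposed by Kenward-Roger"; no empirical (sandwich) standard error is mentioned.

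The mean model is flexible: "The model will include treatment group (as randomized in the parent study), visit, and treatment-by-visit interaction as fixed effects", plus baseline LCI2.5 and screening weight. The outputs are LS means by visit within each parent-study group, with SE and 95% CI, and a plot of LS mean ± SE. Protocol 12.3.3.2 agrees: "The least squares (LS) mean estimate with a 2-sided 95% CI at each visit will be provided".

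LCI2.5 is analysed by a similar MMRM (SAP 8.3.2.2). For ppFEV1 and for CFQ-R, SAP 8.3.3.2 says: "Analysis of this endpoint will be based on an MMRM similar to the analysis of the absolute change in SwCl". I read this as carrying the fallback over to all four endpoints, since nothing else is stated.

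SAP 8.3.2.3 plans no sensitivity or supportive analysis for the secondary endpoints. Descriptive summaries of raw values and changes are planned for all four endpoints.

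**The concern.** The plan goes from the most flexible covariance to nearly the most restrictive. Compound symmetry has two parameters, one variance and one covariance. It treats the Week 4 to Week 8 correlation as equal to the Week 4 to Week 96 correlation, although the visits are 4 weeks apart at the start and up to 24 weeks apart later.

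The model-based output is a set of visit-specific estimates with their precision. Under compound symmetry those SEs would differ between visits essentially only through missing data. Kenward-Roger does not repair this: it allows for estimating the covariance parameters within the assumed structure, not for the structure being wrong. Later visits are of particular interest in a 96-week extension, and an end visit is where a pooled variance can be furthest from the truth if spread changes steadily over time.

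**Working it through.** The documents state no visit SD, correlation, CI width or power, so there is no planned figure to reproduce. The expected 108 subjects are a roll-over number, not a power calculation.

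**Parameter counts.** SAP Appendix A gives 7 post-baseline visits for SwCl, LCI2.5 and CFQ-R (Weeks 4, 8, 16, 24, 48, 72, 96). Spirometry has 10 (also Weeks 36, 60, 84), not counting Safety Follow-up. Unstructured parameters = p(p+1)/2: 7×8/2 = 28 and 10×11/2 = 55, against 2 for compound symmetry.

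**Closed form, complete data.** The compound-symmetry variance then equals the average of the visit variances. So:

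- SE ratio at a visit (model/true) = √(mean visit variance) / SD at that visit
- coverage of the nominal 95% CI = 2Φ(1.96 × SE ratio) − 1

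*Assumption:* the SD is 1 at Week 4 and moves linearly in time to r at Week 96. With f = (week − 4)/92, the mean variance is 1 + 2(r−1)·mean(f) + (r−1)²·mean(f²).

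- 7 visits: mean(f) = 240/(7×92) = 0.3727; mean(f²) = 15584/(7×92²) = 0.2630
- 10 visits: mean(f) = 408/(10×92) = 0.4435; mean(f²) = 26144/(10×92²) = 0.3089

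Example, r = 1.5 and 7 visits: mean variance = 1 + 0.3727 + 0.25×0.2630 = 1.438; SE ratio at Week 96 = √1.438/1.5 = 0.80; coverage = 2Φ(1.567) − 1 = 88.3%.

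| SD change, Week 4 to 96 | SE ratio Week 96, 7 visits | Coverage Week 96, 7 visits | Coverage Week 96, 10 visits | Coverage Week 4, 7 visits |
|---|---|---|---|---|
| −20% | 1.16 | 97.7% | 97.5% | 93.1% |
| 0 | 1.00 | 95.0% | 95.0% | 95.0% |
| +20% | 0.90 | 92.1% | 92.5% | 96.5% |
| +50% | 0.80 | 88.3% | 89.3% | 98.1% |
| +100% | 0.71 | 83.5% | 85.4% | 99.5% |

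The two ends err in opposite directions. The shape matters somewhat: if the SD rises in equal steps per visit instead, Week 96 coverage with 10 visits is 92.8%, 90.0% and 86.7% for +20%, +50% and +100%.

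**Simulation with dropout.** REML compound symmetry, group-by-visit means, 7 visits, 54 per group, 600 replicates, 15% monotone dropout. Group size, dropout and correlations are assumptions. Week 96 coverage was:

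- true correlation 0.6 between all visits: 97.9% (r = 0.8), 96.2% (r = 1.0), 92.7% (r = 1.25), 88.5% (r = 1.5)
- correlation decaying as 0.7 per 24 weeks: 97.6% (r = 0.8), 93.8% (r = 1.0, SE ratio 0.95), 91.1% (r = 1.25)

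Simulation error is about √(0.95×0.05/1200) = 0.6 percentage points (two group intervals per replicate). Dropout therefore leaves the closed-form picture largely unchanged. Decaying correlation with dropout adds at most a small shortfall at constant variance.

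**The case against.** A reader might infer that the fallback makes the Week 96 intervals too narrow. The documents do not support a fixed direction. They give no variances by visit, and the table shows intervals that are too wide if the spread falls and correct if it is constant. An appeal to growing children is not decisive either: ppFEV1 is scaled by age- and height-specific predictions, CFQ-R scores are bounded at 0 and 100, and SwCl values below 10 or above 160 mmol/L are set to missing. This objection stands.

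A reader might also infer from 55 parameters and about 108 subjects that non-convergence is likely. That does not follow. Complete data would give 108×10 = 1,080 observations, the 55-parameter case is ppFEV1 only, and no convergence rate has been estimated. Some incomplete visit patterns are built in: LCI2.5 is missing with a single acceptable replicate, washout tests cannot be done at in-home visits, and the main ppFEV1 analysis uses clinic data only. They make non-convergence a contingency worth planning for, as the SAP itself does, but they do not give its probability.

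Finally, the consequence is limited. Efficacy is not the primary objective, no efficacy test or decision rule is specified, and the planned descriptive summaries show the SD at each visit whichever covariance is used. That lowers the priority. It does not make the tabulated SEs right if spread differs between visits.

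**Conclusion.** The point holds in conditional form. The one-step drop is in the SAP, and compound symmetry averages away any difference in variance between visits. How far the reported SEs would be off, and in which direction, depends on variances that the documents do not give. For SD changes from −20% to +100%, assuming complete data and linearity in time, Week 96 coverage runs from about 97.7% down to 83.5% with 7 visits, and from 97.5% down to 85.4% with 10. The statement that Week 96 intervals will be too narrow is not supported, nor is the statement that the fallback will probably be used. If the unstructured model converges, nothing is affected. Priority is low to moderate: a cheap improvement to secondary and other endpoints, not a threat to the study's primary safety objective.

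**What to change.** In SAP 8.3.2.2, replace the single fallback by an ordered list that keeps visit-specific variances, taking the first structure that converges. For example: unstructured, then heterogeneous Toeplitz, then heterogeneous first-order autoregressive, then heterogeneous compound symmetry. Use plain compound symmetry only last, with empirical (sandwich) SEs at that step. State that the same order applies to LCI2.5, ppFEV1 and CFQ-R, and report which structure was used for each endpoint. The exact ladder is a matter of choice; what matters is that it is fixed in advance and allows unequal variances.

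The cost is one SAP sentence, which SAP section 3 allows by amendment before database lock, and a few more model fits if the first fails. Kenward-Roger is replaced only if the last step is reached. Sandwich errors correct the SE but not the way a wrong covariance weights incomplete data, which is a further reason to keep that step last.

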8.3.2.3 Sensitivity and Supportive Analysis of Secondary Endpoints

No sensitivity or supportive analysis is planned for the secondary endpoints.

8.3.2.4 Subgroup Analysis

No subgroup analysis is planned for the secondary endpoints.

8.3.3 Analysis of Additional Efficacy Variables

8.3.3.1 Definition of Variables

Percent predicted forced expiratory volume in 1 second (ppFEV₁): Percent predicted FEV₁ is the ratio of FEV₁ (L) and predicted FEV₁ (L), expressed as a percentage. The predicted FEV₁ will be calculated using the Global Lung Function Initiative¹ (GLI). See [Appendix C](#) for more details.

Cystic Fibrosis Questionnaire-Revised (CFQ-R): The CFQ-R^{3,4,5} is a validated CF-specific instrument that measures quality-of-life domains. This study utilizes four different versions of CFQ-R:

- CFQ-R for Children ages 6 to 11
- CFQ-R for Children ages 12 and 13
- CFQ-R for Adolescents and Adults (subjects 14 years and older)
- CFQ-R for Parents/Caregivers (subjects 13 years and younger)

In all four versions, specific question belonging to a domain is scored 1, 2, 3, or 4. The CFQ-R domain score, e.g., physical domain score or respiratory domain score, is defined as a scaled score as follows:

Scaled score for a domain = $100 \times (\text{mean (scores of all questions in the domain)} - 1)/3$,

where the score from a negatively phrased question is first reversed, i.e., reversed score = 5 – actual score, so that 1 always represents the worst condition and 4 the best condition. The (scaled) domain score ranges from 0 (worst condition) to 100 (best condition). The scaled score for a specific domain will not be calculated if more than half of the questions in the domain have missing scores.

The (scaled) domain score from the CFQ-R for Children ages 6 to 11, for Children ages 12 and 13, and for Adolescent and Adults will be pooled within and across subjects for the analysis purpose.

8.3.3.2 Analysis Method

Absolute change in ppFEV₁ from baseline:

Analysis of this endpoint will be based on an MMRM similar to the analysis of the absolute change in SwCl. A descriptive summary of raw values and absolute changes from parent study baseline will also be presented.

The primary analysis will use the spirometry data obtained at clinic only. An additional analysis may be performed to include all available spirometry data obtained at clinic and obtained at home, if the spirometry data obtained at home are assessed to be reasonably consistent with the spirometry data obtained at clinic.

Absolute change in CFQ-R respiratory domain (RD) score from baseline:

Analysis of this endpoint will be based on an MMRM similar to the analysis of the absolute change in SwCl. A descriptive summary of raw values and absolute changes from parent study baseline will also be presented. In addition, the descriptive summary for raw values and the absolute change from parent study baseline of the parent version's CFQ-R RD score will be presented.

8.4 Safety Analysis

The primary objective of the study is the evaluation of long-term safety and tolerability of TC. All safety analyses will be based on the TE Period in the OLE for subjects in the OL-SS. The overall long-term safety profile of study drug will be assessed in terms of the following safety and tolerability endpoints:

- Treatment-emergent adverse events (TEAEs)

- Clinical laboratory values
- Standard 12-lead ECGs
- Vital signs
- Pulse oximetry

Only descriptive analysis of safety will be performed, and no statistical testing will be performed.

8.4.1 Adverse Events

For analysis purposes, AEs will be classified as pretreatment AEs, TEAEs, and post-treatment AEs, defined as follows:

- **Pretreatment AE:** any AE before the first dose of ELX/TEZ/IVA in the TE Period in this OLE study
- **TEAE:** any AE that worsened (either in severity or seriousness) or newly developed at or after the first dose date of ELX/TEZ/IVA in the TE Period in this OLE study
- **Post-treatment AE:** any AE that worsened (either in severity or seriousness) or newly developed after the TE Period in this OLE study

For AEs with missing or partial start dates, if there is no clear evidence that the AEs started before or after study drug treatment, then the AEs will be classified as TEAEs. Details for imputing missing or partial start dates of adverse events are described in [Appendix D](#).

An overview of all TEAEs for the OL-SS during the TE Period will be summarized overall and include the following categories:

- Number of TEAEs (total number of TEAEs only)
- Subjects with any TEAEs
- Subjects with TEAEs by strongest relationship
- Subjects with TEAEs by maximum severity
- Subjects with TEAEs leading to treatment discontinuation
- Subjects with TEAEs leading to treatment interruption
- Subjects with Grade 3/4/5 TEAEs
- Subjects with related TEAEs
- Subjects with serious TEAEs
- Subjects with related serious TEAEs
- Subjects with TEAE leading to death

The frequency counts and percentages, as well as the exposure adjusted event rate, will be presented for the above overview table. The exposure adjusted rate will not be presented for strongest relationship and maximum severity categories.

The following summary tables of TEAEs will be presented overall:

- All TEAEs
- Grade 3/4/5 TEAEs
- TEAEs by strongest relationship
- TEAEs by maximum severity
- TEAEs leading to treatment discontinuation
- TEAEs leading to treatment interruption
- Related TEAEs
- Serious TEAEs
- Related serious TEAEs
- TEAEs leading to death

Summaries will be presented by MedDRA System Organ Class (SOC) and Preferred Term (PT) using frequency counts, percentages (i.e., number and percentage of subjects with an event), and the exposure adjusted event rate (except for summary by strongest relationship and maximum severity). When summarizing the number and percentages of subjects, subjects with multiple occurrences of the same adverse event or a continuing adverse event will be counted once, and only the maximum severity level will be presented in the severity summaries, and the strongest relationship level in the relationship summaries. Missing severity levels will not be included in the Grade 3/4/5 TEAE summaries; missing relationship will be considered as related and included in the related TEAE and related serious TEAE summaries.

An additional summary table in which the frequency counts and percentages as well as the exposure adjusted event rate will be presented for TEAEs during the OL safety period:

- All TEAEs by PT

All AEs, including pretreatment AEs, TEAEs, and post-treatment AEs, will be presented in an individual subject data listing based on the OL-AS. In addition, separate listings containing individual subject adverse event data for TEAEs leading to treatment discontinuation, TEAEs leading to treatment interruption, Grade 3/4/5 TEAEs, SAEs and all deaths will be provided, with a flag indicating the TEAE status for SAEs and deaths.

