13.1.1.4 Adverse Event Severity

The investigator will determine and record the severity of all serious and nonserious AEs. The guidance available at the following website will be consulted: Common Terminology Criteria for Adverse Events (CTCAE), Version 5.0, Cancer Therapy Evaluation Program, http://ctep.cancer.gov/protocolDevelopment/electronic_applications/ctc.htm (Accessed September 2019). When considering the severity of an AE in a pediatric subject, the investigator will consider that reference ranges for pediatric clinical laboratory parameters may differ from those in the CTCAE. The severity of an AE described by a term that does not appear in the CTCAE will be determined according to the definitions in Table 13-1.

Table 13-1 Grading of AE Severity

Classification	Description
Grade 1 (Mild)	Mild; asymptomatic or mild symptoms; clinical or diagnostic observations only; intervention not indicated
Grade 2 (Moderate)	Moderate; minimal, local, or noninvasive intervention indicated; limiting age-appropriate instrumental ADL ^a
Grade 3 (Severe)	Severe or medically significant but not immediately life-threatening; hospitalization or prolongation of hospitalization indicated; disabling; limiting self-care ADL ^b
Grade 4 (Life-threatening)	Life-threatening consequences; urgent intervention indicated
Grade 5 (Death)	Death related to adverse event

Table 13-1 Grading of AE Severity

Classification	Description
Source: http://ctep.cancer.gov/protocolDevelopment/electronic_applications/ctc.htm (Accessed September 2019)	
ADL: activities of daily living; AE: adverse event	
Note: A semi-colon indicates 'or' within the description of the grade.	
^a	Instrumental ADL refer to preparing meals, shopping for groceries or clothes, using the telephone, managing money, etc.
^b	Self-care ADL refer to bathing, dressing and undressing, feeding self, using the toilet, taking medications, and not bedridden.

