13.1.2.2 Reporting and Documentation of Serious Adverse Events

All SAEs that occur after obtaining informed consent through the Safety Follow-up Visit, regardless of causality, will be reported by the investigator to Vertex GPS **within 24 hours of identification**. In addition, all SAEs that occur after the Safety Follow-up Visit and are considered related to study drug(s) will be reported to Vertex GPS **within 24 hours of identification**.

For SAEs that occur after obtaining informed consent through the Safety Follow-up Visit, the SAE Form will be completed for new/initial events as well as to report follow-up information on previously reported events. Investigators are asked to report follow-up information as soon as it becomes available to ensure timely reporting to health authorities.

Please send completed SAE Forms to Vertex GPS via:

Email: [contact] (preferred choice)

[contact]

For technical issues related to submitting the form, contact [contact]

SAEs that occur after the Safety Follow-up Visit and are considered related to study drug(s) will be recorded on the Vertex Clinical Trial Safety Information Collection Form (hereafter referred to as the “SAE Form”) using a recognized medical term or diagnosis that accurately reflects the event. SAEs will be assessed by the investigator for relationship to the investigational study drug(s) and possible etiologies. On the SAE Form, relationship to study drug(s) will be assessed only as related (includes possibly related) or not related (includes unlikely related), and severity assessment will not be required. For the purposes of study analysis, if the event has not resolved at the end of the study reporting period, it will be documented as ongoing. For purposes of regulatory safety monitoring, the investigator is required to follow the event to resolution and report the outcome to Vertex using the SAE Form.

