Incomplete/missing data will not be imputed, unless otherwise specified.

Outliers: No formal statistical analyses will be performed to detect or remedy the presence of statistical outliers, unless specified otherwise.

Multiplicity: There will be no multiplicity adjustment as no hypothesis test is planned for safety analysis, unless otherwise specified.

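### TEAEs with missing severity are left out of the Grade 3/4/5 summaries without exception, so a missing grade can only lower the severe-event count or leave it unchanged

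*SAP*

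**What the plan says.** The rule is in SAP 8.4.1: "Missing severity levels will not be included in the Grade 3/4/5 TEAE summaries; missing relationship will be considered as related". The first half of that sentence leaves an unknown grade out; the second half counts an unknown causality in. Earlier in that section, an AE whose start cannot be placed before or after treatment is classed as treatment-emergent. SAP 8.1 adds the general rule "Incomplete/missing data will not be imputed, unless otherwise specified", and nothing else in the SAP supplies a grade when the field is blank. Protocol 12.3.4.1 has no missing-severity rule.

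Grade 3/4/5 TEAEs have a row in the overview table, a table by SOC and PT, and a listing. The row and the table show subject counts, percentages and an exposure-adjusted event rate.

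On collection, Protocol 13.1.1.4 says: "The investigator will determine and record the severity of all serious and nonserious AEs". Protocol 13.1.1.3 includes severity and outcome among the items documented for each AE, with AEs of enrolled subjects recorded in both the CRF and the source document. Protocol 13.3 has missing data queried with the investigator.

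**The concern.** The SAP resolves an unknown relationship and an unclear start date conservatively. An unknown severity is resolved in the favourable direction, and no reason is given. AEs are part of the primary endpoint, and the safety analysis is descriptive, pooled and without a concurrent control. The counts are themselves the result, and no comparison arm shares the error. A rule that can move one of those counts in only one direction deserves attention even if it seldom operates. It also allows two tables in the same report to disagree about a death.

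**Working it through.** There is no planned figure to reproduce. The check covers direction, size and agreement between tables.

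**Inputs.** About 108 subjects expected (SAP 6.2); 96 weeks of treatment (Protocol 9.3.2). The number of ungraded TEAEs is not given. Below, *x* (subjects with a recorded Grade 3 or higher TEAE) and *m* (further subjects whose only possible Grade 3 or higher TEAE is ungraded) are assumptions.

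**Direction, event level.** The SAP counts events that are Grade 3 or higher and graded. The true count is all events of Grade 3 or higher. A worst-case rule would add every ungraded event. Hence SAP count ≤ true count ≤ worst-case count. Enumerating four events, each truly Grade 1, 3 or 5 and each graded or not (3⁴ × 2⁴ = 1,296 patterns), confirmed this ordering in every pattern. The SAP count was exact in 256 of them, namely those in which no ungraded event was truly Grade 3 or higher. That share is not a probability, because the patterns are not weighted by how likely they are.

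**Direction, subject level.** A subject is counted once. The subject count is too low only if an ungraded event is truly Grade 3 or higher and that subject has no other graded TEAE of Grade 3 or higher. The event rate has no such protection, since each omitted event is lost from its numerator.

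**Size, subjects.** One subject is 1/108 = 0.93 percentage points. The SAP reports *x*/108; the true value lies between *x*/108 and (*x* + *m*)/108.

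| Assumed *x* | SAP rule | Upper bound, *m* = 1 | Upper bound, *m* = 2 |
|---|---|---|---|
| 5 | 5/108 = 4.6% | 6/108 = 5.6% | 7/108 = 6.5% |
| 10 | 10/108 = 9.3% | 11/108 = 10.2% | 12/108 = 11.1% |

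With *m* = 0 the two agree.

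**Size, event rate.** If all 108 subjects complete 96 weeks, exposure is 108 × 96 × 7 / 365.25 = 198.7 patient-years. One omitted event is then 100/198.7 = 0.50 per 100 patient-years, and more if exposure is shorter.

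**Agreement between tables.** Protocol Table 13-1 defines Grade 5 as "Death related to adverse event". Table 13-4 assigns the outcome Fatal when the death is at least possibly related to the AE. Outcome is recorded for every AE separately from severity, so for a fatal AE the grade can reasonably be read from another required field. Under SAP 8.4.1 a fatal TEAE with a blank grade would enter the serious and death tables and be missing from the table that includes Grade 5.

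**The case against.** The strongest reply is that the rule will hardly ever operate. Severity is mandatory, missing items are queried, and the investigator formally approves the CRF (Protocol 13.5). A death is also reportable within 24 hours (Protocol 13.1.2.2). A blank grade would have to survive all of that until lock. This stands, and it is why the point is minor. The asymmetry can also be defended: relationship reduces to related or not related, whereas severity has five grades, so counting every blank as Grade 3 or higher could overstate. That stands too, and the fix does not do it.

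Several stronger readings are tempting but unsupported:

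- **Grave events vanish from the report.** They do not. All AEs are listed, and serious TEAEs, SAEs and deaths have their own tables or listings.
- **Ungraded events are barred from the Grade 3/4/5 listing.** The exclusion names summaries; it says nothing about listings.
- **The CRF is the only source of grade for serious events.** On the SAE Form "severity assessment will not be required", but Protocol 13.1.1.3 also places severity in the source document, so a blank can be resolved there.
- **A life-threatening event is Grade 4 by definition.** Table 13-1 words Grade 4 as "Life-threatening consequences; urgent intervention indicated", while the seriousness criterion in Protocol 13.1.2.1 is immediate risk of death as the event occurred. That section keeps serious and severe apart, and Protocol 13.1.1.2 does not make a Grade 4 laboratory value automatically an SAE. A programmed Grade 4 would replace the investigator's judgement.
- **The severe-event count falls by some fixed proportion.** Any relative figure needs a number of severe cases that the documents do not give.

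One caution applies even to fatal events: Table 13-1 governs only terms absent from the CTCAE, and its wording and the Fatal outcome's are close rather than identical. The correspondence is still direct enough for a default when the grade is blank.

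**Conclusion.** The point holds as a minor one. When severity is missing, the rule in SAP 8.4.1 can understate the Grade 3/4/5 summaries and cannot overstate them, and it permits a death to be absent from the Grade 3/4/5 table. The subject-level shift is bounded by *m* × 0.93 percentage points, assuming 108 dosed subjects. It is zero if no grade is missing or if every ungraded event is Grade 1 or 2. A reader might infer that the severe-event count is biased in fact; the documents show only the direction of a possible error, and their collection requirements suggest it will be small. Other safety outputs do not depend on this rule.

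**What to change.** Replace the missing-severity clause in SAP 8.4.1 with:

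> Missing severity will be queried against source before database lock. A TEAE with missing severity and a fatal outcome is counted as Grade 5. The number of subjects with any remaining TEAE of missing severity is shown in a separate 'severity missing' row or footnote to the Grade 3/4/5 and maximum-severity summaries.

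Do not program Grade 4 from the life-threatening seriousness criterion, and do not place ungraded events in the Grade 3/4/5 listing, where they would be mislabelled. The relationship rule can stay as it is.

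The cost is a short amendment, which SAP section 3 allows before database lock, and one extra row or footnote built from data already collected. The reported severe-event count may become slightly less favourable.
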